- 11. Active, uncontrolled bacterial, fungal, or viral infection, including hepatitis B virus (HBV), hepatitis C virus (HCV), known human immunodeficiency virus (HIV), or acquired immunodeficiency syndrome (AIDS) related illness. In equivocal cases, patients whose viral load is negative may be eligible. HIV seropositive patients who are healthy and low risk for AIDS-related outcomes could be considered eligible. Eligibility criteria for HIV positive patients should be evaluated and discussed with the Sponsor's medical monitor and will be based on current and past CD4 and T-cell counts, history (if any) of AIDS defining conditions (eg, opportunistic infections), and status of HIV treatment.
- 12. Moderate or severe hepatic impairment (ie, Child-Pugh class B or C).
- 13. Any of the following cardiac diseases currently or within the last 6 months as defined by New York Heart Association (NYHA) ≥Class 2:
 - e. Unstable angina pectoris
 - f. Congestive heart failure
 - g. Acute myocardial infarction
 - h. Conduction abnormality not controlled with pacemaker or medication
 - i. Significant ventricular or supraventricular arrhythmias (patients with chronic rate-controlled atrial fibrillation in the absence of other cardiac abnormalities are eligible)
 - j. Clinically relevant electrolyte abnormalities (eg, hypokalemia, hypomagnesemia, hypocalcemia) or family history of sudden unexplained death or long ECG interval measured from the onset of the QRS complex to the end of the T wave (QT) syndrome
- 14. Mean resting QT interval corrected for heart rate (QTc) interval using the Fridericia formula (QTcF) >450 msec/male and >470 msec/female (as calculated per institutional standards) obtained from 3 ECGs ≥1 minute apart at study entry.
- 15. Current treatment with medications that are well-known to prolong the QT interval (Appendix 2).
- 16. Psychological, familial, sociological, or geographical conditions that do not permit compliance with the protocol and/or follow-up procedures outlined in the protocol.
- 17. Patients who are receiving strong cytochrome P450 (CYP) 3A inhibitors or inducers within 14 days prior to first dose of study treatment (see prohibited concomitant medications in Appendix 3).

Investigational Product, Dosage, and Mode of Administration:

RP-6306 will be supplied as immediate-release hard capsules for oral administration. RP-6306 will be orally self-administered with approximately 240 mL (~8 oz) of water after an overnight fast of at least 8 hours. Food and drink will be withheld for at least 1 hour after administration of RP-6306. Patients will be initially instructed to take their dose at approximately the same time in the morning. RP-6306 will be taken QD, on a continuous schedule in each 14-day cycle. If a BID dosing schedule is evaluated, the dose will be approximately an even split and should be taken 12 hours apart with food and drink withheld for at least 2 hours prior to and 1 hour post administration of the evening dose. If tolerability of RP-6306 is limited by continuous dosing, an intermittent dosing schedule of 3 consecutive days on / 4 consecutive days off may be explored as guided by the SRC and should follow the administration recommendations of the continuous schedule.

Irinotecan, leucovorin, and fluorouracil will be supplied as commercially available single-use vials. Initially, irinotecan will be administered IV at 180 mg/m² (100% of the approved dose level) given over 30 to 90 minutes on Day 1 of each 14-day cycle. Leucovorin will be administered concomitantly with irinotecan IV at 400 mg/m² (100% of approved leucovorin dose) given over 30 to 90 minutes on Day 1 of each 14-day cycle. Upon completion of the leucovorin infusion, a 400 mg/m² bolus of fluorouracil IV and then a 2400 mg/m² continuous infusion of fluorouracil (100% of approved fluorouracil dose) over 46 hours (Days 1 and 2 of each 14-day cycle) will be administered.

On Day 1 of each cycle, RP-6306 should be taken 15 minutes to 1 hour prior to the start of irinotecan and leucovorin.

During dose finding, intrapatient dose escalations are allowed at the discretion of the Investigator and with Sponsor approval. The dose of RP-6306 and/or irinotecan in the FOLFIRI regimen may be escalated to a higher dose level only after that dose level has been declared safe and tolerable by the SRC. Dose interruptions and dose reductions to manage toxicities will be allowed and carefully monitored by the Investigator, Sponsor, and SRC.

Duration of Treatment:

Patients will continue treatment until disease progression by RECIST v1.1, AE, Investigator decision, withdrawal of consent, protocol noncompliance, pregnancy, or death. After treatment discontinuation, patients will be followed for survival. Survival Follow-up assessments will be done via telephone (or standard method used by participating centers as agreed upon by the Sponsor) every 3 months (±2 weeks) up to 12 months unless the patient withdraws consent to the study, the study is terminated, the patient dies or is LTFU.

Safety:

All AEs/SAEs in enrolled patients must be recorded regardless of the relationship of the AE/SAE to the study treatment from the date of first dose of study treatment through 30 days after the last dose of study treatment, or the start of new anticancer treatment if earlier than 30 days. SAEs considered related to study treatment are to be reported until the end of the Survival Follow-up Period which is up to 12 months after the last dose of investigational product (IP) or until LTFU, patient withdrawal of consent, or whenever the investigator becomes aware thereafter.

During the Screening Period, all AEs related to study procedures are to be captured from the time ICF is signed to the first dose of study treatment. AEs considered not related to study procedures occurring during the Screening Period are to be captured as medical history.

All AEs experienced by a patient, irrespective of the suspected causality, will be monitored and recorded until the TEAE or SAE has resolved; abnormal laboratory values have normalized, stabilized, or returned to baseline and there is a satisfactory explanation for the changes observed; withdrawal of consent; or the patient is LTFU or has died. Any AE that occurs beyond the reporting period that the Investigator assesses as at least possibly related to RP-6306 and/or FOLFIRI should be reported to Repare Therapeutics.

Tolerability and safety will be evaluated by assessment of AEs, TEAEs, SAEs, DLTs, concomitant medications, PEs, vital signs, clinical safety laboratory evaluations (hematology, chemistry, and urinalysis), ECOG performance status, ECGs, and exposure (including dose interruptions and modification).

Concomitant Medications:

Unless contraindicated, patients may receive atropine 0.25 to 1 mg IV/subcutaneous for cholinergic adverse effects (eg, early diarrhea). Diarrhea should be managed aggressively according to institutional guidelines and may include use of loperamide 4 mg at onset of diarrhea, then 2 mg every 2 hours until the patient is diarrhea-free for 12 hours. This may be combined with diphenoxylate/atropine if not adequately controlled with loperamide alone.

Patients with ileus, fever, or febrile neutropenia should receive antibiotics.

It is recommended that patients receive premedication with antiemetic agents according to institutional guidelines. A common antiemetic regimen includes 10 mg of dexamethasone given in conjunction with another type of antiemetic agent, such as a 5-HT3 blocker (eg, oral ondansetron or granisetron). Physicians should also consider providing patients with an additional antiemetic regimen (eg, prochlorperazine) for subsequent use, as needed.

Concomitant treatment and medication information will be collected from the time the patient signs the ICF until 30 days after their last dose of study treatment. The generic name of the drug (or trade name for combination drugs) must be specified along with the reason for use and duration of treatment. Additionally, all diagnostic, therapeutic, or surgical procedures, whether relating to malignancy or not, should be recorded in the electronic case report form (eCRF) including the date, indication, description of the procedure(s), and any clinical finding.

Any changes in documented, permitted concomitant treatments already being taken at the beginning of the clinical study must be recorded in the eCRF, noting the type of medication, the duration, and indication.

Prohibited Treatments:

Other investigational drugs are prohibited.

Statistical Methods:

Detailed methodology for summary and statistical analyses will be documented in the Statistical Analysis Plan.

Sample Size Calculation:

The maximum total sample size for this study is 104 patients. The maximum sample size for the Dose Finding Phase is 36 evaluable patients per Module (72 patients total if an intermittent dosing schedule is initiated). The population used for determination of DLTs will consist of patients who have met the minimum safety evaluation requirements of the study, and/or who have experienced a DLT at any time during the initial 28 days (2 cycles) of the study. Minimum safety requirements will be met if, during the first 2 cycles of treatment, the patient receives at least 75% of planned total doses of RP-6306 for the evaluated schedule, 100% of planned doses of FOLFIRI, completes all required safety evaluations per Schedule of Assessments, and are observed at least until Day 28 since the first dose of study treatment. Thus, the possible total number per Module may be slightly higher at 40 patients (approximately +10%, 80 total patients). Depending on the toxicity profile of the combination and the number of dose levels required to establish the MTD/RP2D, the actual study sample size may vary. Approximately an additional 24 patients will be planned for backfill cohorts.

Analysis Populations

The following analysis populations will be used:

[figure not shown]
- DLT Evaluable Population for dose decisions will be as defined above.
- The Safety Population, used for the assessment of overall safety and tolerability, will consist of all patients who receive at least one dose of study treatment. Patients will be assessed for safety based on the dose level in which they were enrolled.
- The Efficacy Population, used for the assessment of efficacy, will consist of all patients who have measurable disease, are exposed to at least one dose of study treatment, and have local confirmation of their genomic alterations.
- The PK Population, used for the assessment of PK endpoints, will consist of all
 patients who have sufficient RP-6306, irinotecan, or SN-38 plasma concentration data
 recorded to derive PK endpoints.

Efficacy Analysis:

Approximately 24 additional patients will be enrolled in backfill cohorts ($N \le 8$ per cohort) to further evaluate the safety/tolerability profile in specific patient populations (eg, specific cancer types or patients that are high-risk for toxicities),

The efficacy analysis will be summarized by dose combination and data from the backfill cohorts will be pooled with patients from the Dose Finding Phase that were treated at the RP2D (a minimum of 6 patients are expected to be treated at the RP2D during dose finding) when applicable.

Each cohort will be evaluated for ORR, best overall response rate, CBR, DOR, changes in tumor size, PFS at 6 months, and any available OS at 12 months.

Safety Analysis:

Toxicity will be summarized by grade and type. All AEs will be listed, including the verbatim description, system organ class, and preferred term.

Incidence of TEAEs, treatment-related TEAEs, TEAEs leading to death, SAEs, treatment-related SAEs, TEAEs leading to study treatment discontinuation or interruption, and TEAEs leading to dose modifications will be recorded. Clinically relevant laboratory abnormalities (ie, laboratory abnormalities that result in treatment modification or require intervention) will be recorded as AEs. TEAEs will be further summarized by severity (according to NCI CTCAE version 5.0). Changes in clinical laboratory parameters (eg, hematology, chemistry, urinalysis, etc.), CTCAE graded laboratory toxicities, vital signs, ECOG performance status, PEs, and usage of concomitant medications and procedures will be summarized.

PK Analysis:

PK parameters for RP-6306, irinotecan, and SN-38 will be calculated using noncompartmental analysis or other modeling methods as well as using a population PK model: AUC_{0-last} , C_{max} , and T_{max} , and other parameters as appropriate.

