Patients must have a baseline tumor assessment by computed tomography (CT) or magnetic resonance imaging (MRI) scans of known sites of disease as clinically indicated. Positron emission tomography (PET)/CT may be used as clinically indicated. If the patient has had appropriate imaging scans (eg, routine clinical management) performed within 28 days prior to Cycle 1 Day 1, the results of those scans may be used as Screening tumor assessments, if they are of diagnostic quality and could be evaluated by a study center radiologist. Subsequent post-baseline tumor assessments will be performed following RECIST v1.1 guidelines, preferably in study center, but outside evaluation, if assessed by study radiologist, are acceptable. Response will be assessed by the study Investigator; however, all scans will be retained for a blinded independent central review, if deemed necessary.

For follow-up tumor assessments, CT/MRI scans of all sites of known disease will be performed every 6 weeks (± 7 days) or sooner if clinically indicated, from start of treatment (Cycle 1 Day 1) for the first 3 assessments (\sim first 5 months). Thereafter, tumor assessments will be performed every 9 weeks (± 7 days). Per RECIST v1.1, complete response (CR) or partial response (PR) should be confirmed; tumor imaging for confirmation of response must be performed at least 4 weeks after the first indication of response, ideally at the next scheduled tumor assessment.

Tumor assessment should occur according to study schedule regardless of whether study treatment therapy is interrupted. If a patient discontinues treatment for a reason other than disease progression, withdrawal of study consent, or death, scans should continue at the specified intervals until progression is confirmed or until the start of subsequent anticancer treatment.

Efficacy will be reported as ORR, best overall response rate, CBR, DOR, and best percent change in tumor size from baseline per RECIST v1.1. Available data for PFS at 6 months and OS at 12 months will also be reported.

Laboratory Assessments:

Blood samples will be collected throughout the study to closely monitor safety parameters and characterize the PK profile of RP-6306, irinotecan, and irinotecan's active metabolite (SN-38) when co-administered.

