8.1.4. Clinical Benefit Rate (CBR)

CBR is defined as the proportion of patients with a best overall response of CR or PR according to RECIST v1.1 based on Investigator's assessment or duration on treatment of at least 16 weeks without evidence of progression.

CBR will be defined for patients in efficacy population only.

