8.1.8. Progression Free Survival (PFS)

Progression-Free Survival (PFS) is defined as the time from the first day of study drug administration (Day 1) to disease progression as defined by RECIST v1.1 criteria or death from any cause.

TL, NTL and new lesion assessments may be performed on different dates. The following rules will be applied for determine progression and censoring dates:

Date of progression will be determined based on the earliest of the dates of the component that triggered the progression. For example, if progression was due to a new lesion only then the date of the new lesions would be used. If progression was due to TLs and a new lesion, then the earliest of the TL and new lesion dates would be used.

Patients who are alive and free from disease progression will be censored at the date of their last evaluable tumor assessment prior to or equal to the data cut off date.

Any patient who dies in the absence of progression after 2 or more missed assessments will be censored at the date of their last radiographic tumor assessment. Specifically, if the death date is >12 weeks from the last tumor assessment, the death date will not be used for the calculation of PFS.

If a patient has no baseline tumor assessment/no post dose tumor assessments then they will be censored at 0 days for PFS, unless they died within 12 weeks from the date of first dose (and also before cut-off), in which case their death date will be used as a PFS event.

Table 5 gives the details rules of defining censoring/event for PFS.

PFS at 6 months will be reported based on KM methods as the number and % of patients estimated to be progression free at 6 months.

Table 5: Censoring Rule for time-to-event analyses (PFS) based on radiographical tumor assessment or death

Situation	Date of Censoring or Date of Event	Censor
Documented disease progression (PD) before data cutoff	Date of first PD	0
No PD, but death date is within 12 weeks from the last adequate post-baseline assessment ^a	Date of death	0
No PD, no post-baseline assessment, and death date is within 12 weeks from the date of first dose	Date of death	0
No PD, no post-baseline assessment ^a , and death date > 12 weeks from the date of first dose	Date of the first dose	1
No PD, no post-baseline assessment ^a , and no death	Date of the first dose	1

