8.2. Efficacy Analysis Methods

For overall response rate, ORR, and CBR, the number and percentage of patients along with an exact binomial 95% confidence interval (CI), using the Clopper-Pearson method, will be presented.

In general, summary of all efficacy endpoints will be provided by dose level separately for Module 1a and 1b patients.

The assessment of tumor efficacy will be based on the measurements recorded by the investigator.

A summary of the best objective response will be presented which will include the number and percentage of patients with a best response of CR, PR, SD, PD and NE.

Time-to-event endpoints (PFS) will be analyzed using the KM method and results will be summarized by the 25th, 50th and 75th percentiles, if estimable, with associated 2-sided 95% CIs. KM plots will be provided. For PFS, the number (%) of patients with an event and the number (%) of patients censored will also be presented. The rate of PFS at 16 weeks and 24 weeks will be derived from the corresponding Kaplan-Meier curves. The KM analyses for DOR may be replaced by descriptive summary of median, and quartiles with individual listing for responders if total confirmed responders are few and less than 5 patients.

Maximum reduction in tumor size will be summarized by n, mean, standard deviation, median, 25th quartile and 75th quartile, minimum and maximum. The spider plots displaying change in tumor size over time for each patient will also be provided for each module and dose/schedule group as described above.

In addition, waterfall plots showing the best percentage change from baseline (largest decrease or smallest increase in the absence of a decrease) in the sum of the TL sizes will be produced for each module by dose/schedule group indicating each patient' best objective response.

Swimmer plots will be produced for each module and dose/schedule group to show the duration of study treatment per patient with indicators for timing of response, progression or death, where applicable.

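### Landmark PFS at 16 weeks, 24 weeks and 6 months falls well after the last scheduled scan and reads high; add scan-aligned readings at weeks 19 and 28

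*Protocol*

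**What the plan says.** The Efficacy part of the Protocol Synopsis sets the calendar: "CT/MRI scans of all sites of known disease will be performed every 6 weeks (± 7 days) or sooner if clinically indicated". This 6-weekly interval applies "from start of treatment (Cycle 1 Day 1) for the first 3 assessments", a phase that a bracket describes as roughly five months. The interval then lengthens: "Thereafter, tumor assessments will be performed every 9 weeks (± 7 days". Responses are to be confirmed at least 4 weeks later, ideally at the next scheduled assessment.

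The SAP sets the reading times. Section 8.1.8: "PFS at 6 months will be reported based on KM methods". Section 8.2: "The rate of PFS at 16 weeks and 24 weeks will be derived from the corresponding Kaplan-Meier curves". For patients without a response, Section 8.1.4 counts clinical benefit by "duration on treatment of at least 16 weeks without evidence of progression".

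Section 8.1.8 also fixes the dates that enter the curve: "Date of progression will be determined based on the earliest of the dates of the component that triggered the progression", and "Patients who are alive and free from disease progression will be censored at the date of their last evaluable tumor assessment". The SAP plans no interval-censored analysis and no sensitivity analysis for scan timing.

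**The concern.** None of the reading times falls on or just after a scheduled scan. Progression that begins after the week-18 scan, and that no unscheduled scan picks up, is not dated until about week 27. By then the 24-week reading has passed, and usually the 6-month reading too. The same happens to the 16-week reading between the week-12 and week-18 scans. The curve stays flat over these stretches except for deaths and unscheduled findings, so the landmark rate is close to the rate at the previous scan.

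PFS at 6 months and CBR are named secondary endpoints. The study is single-arm, so the figures will be set against outside data from studies whose scan calendars may differ. Preliminary efficacy is also one of the inputs to the choice of RP2D and schedule. A reader who takes the 6-month figure at face value would credit the combination with some progression-free time that nobody observed.

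**Working it through.** **The protocol's own figure.** Three assessments at 6-week intervals take 3 × 6 = 18 weeks. At 4.348 weeks per month that is 18 / 4.348 = 4.1 months, not about 5. Even if every interval ran 7 days long, 21 / 4.348 = 4.8 months. The slip does not change the calendar: 5 months is 21.7 weeks and still holds only the week 6, 12 and 18 scans. The fourth scan is at 18 + 9 = week 27.

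**Age of the last scheduled scan at each reading**
- 16 weeks: 16 − 12 = 4 weeks.
- 24 weeks: 24 − 18 = 6 weeks.
- 6 months: 26.1 − 18 = 8.1 weeks.

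On nominal dates, 24-week and 6-month PFS rest on the same scan, although the readings are 2.1 weeks apart.

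**Size.** The documents give no PFS assumption, so the following are assumed:
- True PFS is exponential, S(t) = 0.5^(t/m), with median m of 12 to 30 weeks.
- Scan dates are uniform within ±7 days of the Day-1 calendar, and there is no dropout.
- A fraction f of events carries its exact date (deaths, clinically indicated scans); the rest are dated at the next scheduled scan.

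With L(t) the date of the last scan at or before t, the Kaplan-Meier reading is

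R(t) = f·S(t) + (1 − f)·E[S(L(t))].

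Example: m = 16 weeks, f = 15%, t = 26.09 weeks. True S = 32.3%. The week-27 scan has been done by then with probability (26.09 − 26)/2 = 4.5%; otherwise the week-18 scan is the latest. E[S(L)] = 0.955 × 45.9% + 0.045 × 32.4% = 45.3%. R = 0.15 × 32.3% + 0.85 × 45.3% = 43.3%. The excess is 11.0 points.

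| Median (weeks) | True PFS at 6 months | Read, f = 15% | Read, f = 40% | Excess at 24 weeks (15% / 40%) | Excess at 16 weeks (15% / 40%) |
|---|---|---|---|---|---|
| 12 | 22.2% | 32.9% | 29.7% | 8.8 / 6.2 | 8.8 / 6.2 |
| 16 | 32.3% | 43.3% | 40.1% | 8.9 / 6.3 | 8.1 / 5.7 |
| 20 | 40.5% | 51.1% | 48.0% | 8.6 / 6.0 | 7.3 / 5.1 |
| 24 | 47.1% | 57.1% | 54.2% | 8.0 / 5.7 | 6.6 / 4.6 |
| 30 | 54.7% | 63.9% | 61.2% | 7.3 / 5.1 | 5.7 / 4.0 |

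The excess at 6 months is 9 to 11 points with f = 15% and 6 to 8 with f = 40%.

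**Reading when a scan window has closed.** With the same model, the excess at week 19 is 1.3 to 1.7 points (f = 15%) or 0.9 to 1.2 (f = 40%). At week 28 it is 1.0 to 1.1 or 0.7 to 0.8.

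**Anchor of the 9-weekly scans.** The Synopsis ties only the first three scans to Cycle 1 Day 1. If the fourth is timed from the third, its date is 27 plus the sum of two uniform ±1-week deviations. The chance that it falls after week 28 is (2 − 1)²/8 = 12.5%, and it cannot fall after week 29. The week-28 excess is then 2.4 to 2.8 points (f = 15%), and the week-29 excess is 2.0 to 2.2.

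**The case against.** Several objections stand.

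- A reader might infer that no scan at all can happen between weeks 12 and 18 or between 18 and 27. The documents do not support that. Scans may be done sooner if clinically indicated (wording attached to the 6-weekly phase), and response confirmation is possible from 4 weeks. The gaps are between scheduled scans. Unscheduled scans shrink the excess, which is why the 40% column is shown; they do not remove it.
- Dating progression at the assessment that shows it is the usual convention and is specified. A patient with progression at week 18 who was on treatment at week 16 without evidence of progression meets the CBR definition as written. High here means relative to true progression status; the SAP's rule is not misapplied.
- A reader might also infer that Section 8.2 replaces 6 months with 24 weeks. It does not: SAP 2.1 and 8.1.8 keep the 6-month endpoint, and 8.2 adds two readings.
- Groups are small. With 6 patients at the RP2D and a backfill cohort of 8, a result of 7/14 has an exact 95% interval of 23% to 77%, far wider than the excess. All dose levels also share the same calendar, so comparisons between them are little affected.
- Moving the 6-month endpoint to week 28, or redefining CBR, would change protocol endpoints. Part of any drop would come only from reading later: at a 16-week median, true PFS falls from 32.3% at 6 months to 29.7% at week 28.

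These points argue for adding readings beside the planned ones and leaving the endpoints alone. They do not remove the upward shift. The SAP already aligns one category with a scan window: Section 8.1.6 accepts stable disease from Day 35, that is, 6 weeks less 7 days.

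**Conclusion.** The concern holds as an interpretive bias in descriptive secondary endpoints. As planned, 6-month and 24-week PFS mostly report week-18 status, and 16-week PFS mostly reports week-12 status. The excess over true PFS is about 6 to 11 points at 6 months, 5 to 9 at 24 weeks and 4 to 9 at 16 weeks. It rests on assumed exponential medians of 12 to 30 weeks and on 15% or 40% of events being dated between scheduled scans. The upward direction does not depend on the particular median.

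CBR is touched only through its route for non-responders; patients counted through CR or PR are not affected. Its excess cannot be taken from the PFS figures and is not quantified.

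A reader might go further and infer that dose finding or the RP2D is compromised. The documents do not support that: escalation rests on DLTs, no hypothesis is tested, and the RP2D draws on safety, PK, pharmacodynamics and efficacy together. The Schedule of Assessments (Protocol Section 12.1) is not in the public text, so the calendar used here is the one in the Synopsis.

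**What to change.** Keep the scan schedule and the protocol's 6-month endpoint.

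1. In SAP 8.1.8 and 8.2, add Kaplan-Meier PFS at week 19 and week 28, after the week-18 and week-27 windows close, as the scan-aligned readings. Report them beside the 16-week and 6-month figures, and state that those two rest on the week-12 and week-18 scans.
2. Drop the 24-week reading or explain it, since it repeats the week-18 information.
3. State that the 9-weekly scans are timed from Cycle 1 Day 1. If they are timed from the previous scan, read at week 29 instead of week 28.
4. Leave the CBR definition in SAP 2.2.2 and 8.1.4 unchanged. Add a supportive count in which a non-responder must also have no progression at the week-18 scan (Day 119 or later: 126 − 7), with a patient who has no such scan counted as no benefit.
5. In the Protocol Synopsis, reconcile the five-month bracket with 18 weeks (about 4 months).

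The cost is SAP wording, a few extra table rows and one corrected bracket; no scans are added. The added figures will be somewhat lower, partly because they are read 2 to 3 weeks later, and the report should say so.
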